2. INTRODUCTION

This statistical analysis plan (SAP) describes the analyses and data presentations for Celgene's protocol GED-0301-CD-004 "A Phase 3, Long-term Active Treatment Extension Study of Mongersen (GED-0301) in Subjects with Crohn's Disease" as amended on 06 Jan 2017. It contains definitions of analysis populations, derived variables and statistical methods for the analysis of efficacy and safety.

The study was terminated early by Celgene following an October 2017 recommendation of the Data Monitoring Committee. As such, changes are made to some protocol-specified analyses; these changes are described in relevant sections and summarized in Section 16.

In this SAP, GED-0301 160 mg once daily (QD), GED-0301 40 mg QD, and placebo QD are referred to as GED 160, GED 40, and PBO, respectively. Subjects will be assigned to receive one of 5 GED-0301 treatment regimens during the study, based on the treatment received during the core GED-0301 Phase 3 study (GED-0301-CD-002), and whether the subject met the clinical improvement criteria. For the first 12 weeks of the study, subjects will receive blinded, active GED-0301 treatment as one of the following numbered treatment groups:

- 1) continuous GED 160 for 12 weeks;
- 2) GED 160 for 4 weeks, PBO for 4 weeks, GED 160 for 4 weeks;
- 3) PBO for 4 weeks, GED 160 for 4 weeks, PBO for 4 weeks;
- 4) continuous GED 40 for 12 weeks;
- 5) PBO for 4 weeks, GED 40 for 4 weeks, PBO for 4 weeks.

Beginning at Week 12 through Week 208, subjects from the above-numbered treatment groups will continue to receive blinded, active GED-0301 treatment for 196 weeks as the following:

- 1) alternating PBO for 4 weeks and GED 160 for 4 weeks, through Week 208;
- 2) alternating PBO for 4 weeks and GED 160 for 4 weeks, through Week 208;
- 3) alternating GED 160 for 4 weeks and PBO for 4 weeks, through Week 208;
- 4) continuous GED 40, through Week 208;
- 5) alternating GED 40 for 4 weeks and PBO for 4 weeks, through Week 208.

The treatment regimens of alternating GED 160 for 4 weeks and PBO for 4 weeks (irrespective of whether GED 160 or PBO is administered first in this extension study), continuous GED 40, alternating GED 40 for 4 weeks and PBO for 4 weeks, are referred to as GED 160 ALT, GED 40, and GED 40 ALT, respectively. Investigational product (IP) refers to GED 160, GED 40, or PBO.

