4. INVESTIGATIONAL PLAN

4.1. Overall Study Design and Plan

To streamline this SAP, the Study Design section of the protocol is copied below, with the understanding that the references to Study GED-0301-CD-003 are no longer applicable since the study was not initiated before the study termination.

This is a Phase 3, double-blind, long-term active treatment extension study to evaluate the long-term safety [REDACTED] of GED-0301 for 208 weeks in adult and adolescent subjects with CD who previously participated in either of the following two Phase 3 GED-0301 studies:

- Study GED-0301-CD-002 (Adult Subjects)
- Study GED-0301-CD-003 (Adult and Adolescent Subjects)

The purpose of this study is to assess long-term safety data of GED-0301 for a period of up to 208 weeks in adult subjects (ie, ≥ 18 years of age) who participated in the core Phase 3 GED-0301-CD-002 and GED-0301-CD-003 studies and adolescent subjects (ie, 12 to 17 years of age) who participated in the core Phase 3 GED-0301-CD-003 study.

Although all subjects will receive active treatment, this study is double-blinded for the entire 208 weeks for the purpose of preserving the blind of the subject's treatment allocation in the initial, core Phase 3 GED-0301 study.

Subjects from Study GED-0301-CD-002 who completed the study at Week 52, or who met the early escape criteria (Appendix H of the protocol) and were discontinued during the time period beginning at Week 12 through Week 52, may be eligible to enter this study.

Subjects from Study GED-0301-CD-003 who completed the study at Week 12 may also be eligible to enter this long-term active treatment study.

Subjects who discontinued Studies GED-0301-CD-002 or GED-0301-CD-003 prior to the Week 12 Visit are not eligible for this study.

This long-term active treatment study will consist of 3 periods:

- Screening Period – up to 4 weeks (ie, 1 day to 28 days depending on when long-term active treatment is available for the subject at the study center)
- Long-term Active Treatment Period – 208 Weeks (Week 0 to Week 208)
- Follow-up Period – 4 weeks (ie, no IP taken)

At Week 12, subjects will be evaluated to determine if they should be discontinued from the study based on clinical criteria. Subjects, who meet the following criteria, will be discontinued from the study at Week 12:

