4.3. Stratification, Randomization, and Blinding

There is no randomization or stratification in this study. Eligible subjects will be assigned via an IRTS to receive one of 5 double-blind GED-0301 treatment regimens (Section 2) during the study, based on the treatment received during the initial, core GED-0301 Phase 3 study, and whether the subject met the clinical improvement criteria.

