5. GENERAL STATISTICAL CONSIDERATIONS

5.1. Treatment Grouping Approaches

In listings, treatment will be displayed in 5 treatment regimens (corresponding to the 5 numbered treatment groups in Section 2), as follows:

- GED 160 12WK/PBO/GED 160 ALT
- GED 160/PBO ALT
- PBO/GED 160 ALT
- GED 40
- PBO/GED 40 ALT

The following treatment grouping will be used in tables.

- GED 40 ALT
- GED 40
- GED 160 ALT (combining all variants of this regimen)
- GED Total

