12.3. Clinical Laboratory Evaluations

The following protocol-specified parameters from the central laboratory will be summarized:

- Hematology panel will include: complete blood count (CBC) with differential, including red blood cell (RBC) count, hemoglobin, hematocrit, mean corpuscular hemoglobin (MCH), mean corpuscular hemoglobin concentration (MCHC), mean corpuscular volume (MCV), white blood cell (WBC) count (with differential), and platelet count.
- Serum chemistry panel will include: total protein, albumin, calcium, phosphorous, glucose, total cholesterol, triglycerides, uric acid, total bilirubin, alkaline phosphatase, aspartate aminotransferase (AST)/serum glutamic oxaloacetic transaminase (SGOT), alanine aminotransferase (ALT)/serum glutamic pyruvic transaminase (SGPT), sodium, potassium, magnesium, chloride, carbon dioxide, blood urea nitrogen (BUN), creatinine, and lactic dehydrogenase (LDH), .
- Coagulation assessment will include: prothrombin time and activated partial thromboplastin time (APTT)
- Complement activation factor panel will include: compliment activation factors Bb, C3a and C5a.
- Urinalysis will include specific gravity and pH.

Summary statistics of observed values and changes from baseline will be provided by time point (time points include the scheduled visits for labs, the follow-up visit, and the end of Weeks 0-208).

Frequency summaries (shift tables) of shifts from baseline to post-baseline time points (time points include the scheduled visits for labs, the end of Weeks 0-208, and the worst value of Weeks 0-208) by category of low/normal/high/both low and high (the last category for the shift to the worst value only) will be provided for hematology and serum chemistry.

A summary of laboratory marked abnormalities as defined in Section 18.1 will be provided for Weeks 0-208.

A separate summary of laboratory marked abnormalities will also be presented by normal baseline and abnormal baseline.

A subject data listing of all laboratory data (including urinalysis) will be provided.

[figure not shown]

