12.4. Vital Signs and Body Weight

For vital signs and body weight, summary statistics of observed values and changes from baseline (also percent change from baseline for body weight) will be provided by time point (time points include the scheduled visits for vital signs/body weight, the follow-up visit, and the end of Weeks 0-208).

A subject data listing of all vital signs and body weight will be provided.

[figure not shown]

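### By-visit lab and vital-sign tables pool 160 mg subjects who have just finished opposite 4-week blocks, without showing the mix

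*SAP*

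**What the plan says.** SAP 2 defines five regimens. Three are 160 mg regimens: regimen 1 (160 mg for 12 weeks, then alternating from a placebo block), regimen 2 (alternating, 160 mg first) and regimen 3 (alternating, placebo first). Regimens 1 and 2 are called GED-first below and regimen 3 PBO-first. The label GED 160 ALT applies "irrespective of whether GED 160 or PBO is administered first in this extension study". SAP 5.1 keeps the five regimens apart in listings, but tables have one column for all 160 mg subjects ("GED 160 ALT (combining all variants of this regimen").

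For laboratory data, SAP 12.3 says "Summary statistics of observed values and changes from baseline will be provided by time point". For vital signs and weight, SAP 12.4 says "summary statistics of observed values and changes from baseline (also percent change from baseline for body weight) will be provided by time point". No visible text splits or labels these summaries by the block just completed.

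The study stopped early, "following an October 2017 recommendation of the Data Monitoring Committee". SAP 4.1 adds that "references to Study GED-0301-CD-003 are no longer applicable since the study was not initiated before the study termination". The adult schedule (Protocol Table 5) and the CD-002 rows of Appendix G are therefore the ones that matter.

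**The concern.** Two subjects in the same GED 160 ALT cell at the same visit can differ in what they took over the previous four weeks: one 160 mg daily, the other placebo daily. A by-visit mean then averages after-drug and after-placebo values in a proportion the table does not report. The assessment schedule does not even this out, because visits fall unevenly on the 8-week cycle.

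Long-term safety is the primary objective, and these are among its planned summaries. If a drug effect on a laboratory value or vital sign appears and reverses within about four weeks, the pooled mean understates it. The understatement changes from visit to visit, so a constant effect can look as though it waxes and wanes.

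**Working it through.** **Inputs.** Dispensing by week: Protocol Tables 7-10, which give what is handed out at each visit. Timing: Protocol 6.2, evaluations before dosing on the visit day. Adult assessment weeks: Protocol Table 5. The plan gives no figure of its own to reproduce.

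**Rule.** The block just finished at Week w is the one dispensed at Week w - 4. Year 1 vital-sign and weight visits:

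| Visit | Dispensed at | Regimen 1 | Regimen 2 | Regimen 3 |
|---|---|---|---|---|
| 4 | 0 | 160 | 160 | PBO |
| 8 | 4 | 160 | PBO | 160 |
| 12 | 8 | 160 | 160 | PBO |
| 16 | 12 | PBO | PBO | 160 |
| 24 | 20 | PBO | PBO | 160 |
| 32 | 28 | PBO | PBO | 160 |
| 40 | 36 | PBO | PBO | 160 |
| 48 | 44 | PBO | PBO | 160 |
| 52 | 48 | 160 | 160 | PBO |

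Over all 52 on-treatment visits (Weeks 4 to 208), regimens 2 and 3 are opposite at 52 and regimens 1 and 3 at 51; the exception is Week 8.

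**Year 1 visits that follow an active block, GED-first v PBO-first.**
- Vital signs and weight: 3 of 9 (regimen 2) or 4 of 9 (regimen 1) v 6 of 9.
- Hematology (Weeks 4, 8, 12, 24, 40, 52): 3-4 of 6 v 3 of 6.
- Chemistry, coagulation, complement and urinalysis (Weeks 12, 24, 40, 52): 2 of 4 (Weeks 12, 52) v 2 of 4 (Weeks 24, 40).

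The Week 40 adult labs carry a footnote whose text is not shown. Without Week 40, the last two lines become 3-4 of 5 v 2 of 5, and 2 of 3 v 1 of 3.

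**Later visits.** In Year 2, every vital-sign visit (Weeks 56 to 104, every 8 weeks) and both lab visits (Weeks 80, 104) follow placebo for GED-first subjects and active drug for PBO-first subjects. How many subjects reached these visits is not given.

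**Illustration for observed values.** Let d be a constant on-drug shift, c the share of d left at the end of a placebo block, and q the PBO-first share of the column. At Weeks 12 and 52 the pooled shift is d[(1 - q) + qc]; at Weeks 24 and 40 it is d[(1 - q)c + q].

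The documents do not give q. In Appendix G, six CD-002 rows feed GED 160 ALT and only one is PBO-first: 160 mg alternating, improved at Week 52. Assume four equal core arms, a common improvement rate p, and everyone entering. Then PBO-first = p, GED-first = 1 + 3(1 - p), and q = p / (4 - 2p). For p = 20, 40, 60, 80 and 100%, q = 6, 13, 21, 33 and 50%.

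| q | Weeks 12, 52 (c = 0) | Weeks 24, 40 (c = 0) | Weeks 12, 52 (c = 0.5) | Weeks 24, 40 (c = 0.5) |
|---|---|---|---|---|
| 6% | 94% | 6% | 97% | 53% |
| 13% | 88% | 13% | 94% | 56% |
| 21% | 79% | 21% | 89% | 61% |
| 33% | 67% | 33% | 83% | 67% |
| 50% | 50% | 50% | 75% | 75% |

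Entries are the pooled shift as a share of d. Unequal entry or dropout would move q off this range. The table does not carry over to change from baseline, because the visible SAP does not define the laboratory baseline.

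**The case against.** The pooling is stated openly in SAP 2 and 5.1, p-values are excluded, and the listings allow the split to be rebuilt. Clinically significant laboratory results not tied to a diagnosis are recorded as adverse events (Protocol 6.5.3, 6.5.4, 10.3), and these are summarized over the whole of Weeks 0-208. Hematology and chemistry also have worst-value shift tables. Neither view depends on block phase. Protocol 1.2.2.1 calls systemic bioavailability negligible, from 7-day data up to 160 mg/day, and nothing shows that body weight would swing in 4-week blocks. On Appendix G, the PBO-first share may well be low, which would make the column nearly single-phase.

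Most of this stands and lowers the weight of the point. It does not remove it. The worst-value shifts do not cover coagulation, complement, vital signs or weight, and modest reversible shifts in means need not become adverse events. A low PBO-first share does not rescue the by-visit reading either: the column would then be mostly after-placebo at Weeks 24, 40, 80 and 104, without saying so.

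A reader might go further in two directions that the documents do not support. One is to treat the gap between GED 160 ALT and GED 40 ALT as a biased dose comparison. The SAP plans no such comparison, "There is no randomization or stratification in this study", and the columns differ in core-study treatment and response. The other is to infer that treatment duration in SAP 9.1 overstates time on drug, because "Investigational product (IP) refers to GED 160, GED 40, or PBO". The duration formula is not visible, so that cannot be established.

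**Conclusion.** The point holds as a weakness of presentation, not as an error or contradiction. The phase pattern follows from the planned dispensing and visit schedule. The consequence depends on assumptions: a laboratory or vital-sign effect exists, it largely reverses within about four weeks, and subjects kept to the planned blocks. Under those assumptions the pooled observed mean could show anywhere from a small part to nearly all of the effect, depending on the visit. The actual size is unknown and may be small.

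The documents do not support saying that the plan would hide a major safety problem, given adverse-event recording and the worst-value shifts. The follow-up visit is unaffected, since all subjects are then four weeks off investigational product. SAP 12.1, 13-14 and 18 are not visible, so a split defined there cannot be excluded.

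**What to change.** In SAP 12.3 and 12.4, add supportive, descriptive by-visit summaries for GED 160 ALT and GED 40 ALT by active or placebo status of the preceding 4-week block. At the least, split GED 160 ALT into GED-first and PBO-first, with n at each visit. Within GED 160 ALT the two splits form the same groups at every visit except Week 8, where regimen 1 follows an active block. Status labels have the advantage of also explaining a swing from visit to visit within a column. GED 40 ALT is PBO-first throughout, so its subjects share one status at each visit and need only the label.

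Mark these summaries non-causal. By Appendix G, PBO-first subjects are GED-treated improvers, while GED-first subjects are GED-treated non-improvers or former placebo subjects; carry-over is also possible.

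This is a cheap, low-priority improvement: SAP wording and a few extra tables from dispensing data already recorded. The cost is smaller cells.

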12.4. Vital Signs and Body Weight

For vital signs and body weight, summary statistics of observed values and changes from baseline (also percent change from baseline for body weight) will be provided by time point (time points include the scheduled visits for vital signs/body weight, the follow-up visit, and the end of Weeks 0-208).

A subject data listing of all vital signs and body weight will be provided.

[figure not shown]
12.5. Electrocardiogram

A frequency summary (shift table) of the shift from baseline to the end of Weeks 0-208 in investigator clinical interpretation of ECG (normal; abnormal, not clinically significant; and abnormal, clinically significant) will be provided.

CEL GENE PROPRIETARY INFORMATION

CELGENE PROPRIETARY INFORMATION

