6.5.2. Electrocardiogram

Subjects will have a 12-lead ECG at the frequency specified in Table 5 and Table 6. Sites are to utilize their own local ECG machines and the automated ECG readings will be further interpreted by the Investigator by clinically correlating them with the subject’s condition. The Investigator’s clinical interpretation will be recorded in the eCRF as: normal; abnormal, not clinically significant; or abnormal, clinically significant. “Abnormal, clinically significant” results if not related to medical condition or diagnosis, should be recorded as an AE on the AE eCRF.

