6.5.4. Clinically Significant Abnormal Findings

Clinically significant abnormal findings or results (clinical laboratory assessments, physical examinations, ECGs) if not related to a medical condition or diagnosis, which are identified prior to the very first dose of IP taken from the core study, should have been recorded on the Medical History eCRF in the core Phase 3 study. Clinically significant abnormal findings or results, not related to a medical condition or diagnosis, during this study should be recorded as AEs on the AE eCRF. Any clinically significant abnormal findings or results related to the disease under study, CD, should not be recorded as an AE on the AE eCRF. Only if CD meets any of the criteria as an SAE, is it recorded on the AE eCRF.

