9.7. Safety Analysis

Safety will be assessed by clinical review of all relevant parameters including treatment-emergent adverse events (TEAEs), laboratory tests, vital signs, weight, and ECGs. No inferential testing for statistical significance will be performed.

Treatment-emergent adverse events will be classified using the MedDRA classification system. All TEAEs will be summarized by system organ class, preferred term, severity, and relationship to IP. The TEAEs leading to death or to discontinuation from treatment and serious TEAEs will also be tabulated. In the by-subject analysis, a subject having the same event more than once will be counted only once and by greatest severity.

Laboratory, vital signs, weight, and ECG data will be summarized descriptively by time point. In addition, shift tables showing the number of subjects with values low, normal, and high compared to the normal ranges at baseline versus postbaseline will be provided for laboratory tests.

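### The protocol promises ECG summaries by time point, but the visible SAP tabulates only the shift to the end of Weeks 0-208, so earlier on-treatment ECG readings enter no visible ECG table

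*SAP*

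**What the plan says.** Protocol 9.7 names the safety parameters for clinical review, among them "laboratory tests, vital signs, weight, and ECGs". It then sets one rule for four of them: "Laboratory, vital signs, weight, and ECG data will be summarized descriptively by time point". The Statistical Methods part of the Protocol Summary repeats the rule.

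The SAP implements it as follows.

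- **Laboratory data (SAP 12.3).** Observed values and changes are given at each scheduled visit, at follow-up and at the end of Weeks 0-208. Shift tables for hematology and chemistry use these points: "time points include the scheduled visits for labs, the end of Weeks 0-208, and the worst value of Weeks 0-208".
- **Vital signs and weight (SAP 12.4).** "time points include the scheduled visits for vital signs/body weight, the follow-up visit, and the end of Weeks 0-208".
- **ECG (SAP 12.5).** "A frequency summary (shift table) of the shift from baseline to the end of Weeks 0-208 in investigator clinical interpretation of ECG". The visible section names no scheduled visit, worst reading or ECG listing.

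The data come from Protocol 6.5.2, where the investigator's "clinical interpretation will be recorded in the eCRF as: normal; abnormal, not clinically significant; or abnormal, clinically significant". Table 5 (adults) and Table 6 (adolescents) schedule these ECGs at screening, at Weeks 12, 24, 52, 104, 156 and 208, and at early termination. None is scheduled at the Follow-up Visit.

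**The concern.** Long-term safety is the study's primary objective, and ECG is one of the parameters on which Protocol 9.7 says it will be judged. A table that compares baseline only with the end of the period cannot show what happened in between. A subject whose ECG was abnormal at Week 12 or Week 24 and normal at the last reading appears as normal.

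In SAP 12.3 and 12.4 the end of Weeks 0-208 is listed in addition to the scheduled visits, so in the SAP's own usage it does not stand for them. For hematology and chemistry the SAP also guards against transient abnormalities with a shift to the worst value. ECG has neither the visits nor the worst value.

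What is at stake is a count of ECG interpretations at each visit, with its denominator. In particular, a transient reading classed as abnormal but not clinically significant enters no visible table.

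**Working it through.** The plan gives no figure to reproduce. The check compares the texts and counts the scheduled ECGs.

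**Step 1: rule against implementation.**

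| Parameter | Protocol 9.7 | Scheduled visits in SAP | End of Weeks 0-208 in SAP | Worst value in SAP |
|---|---|---|---|---|
| Hematology, chemistry | by time point | yes | yes | yes (shift) |
| Vital signs, weight | by time point | yes | yes | no |
| ECG | by time point | none visible | yes | none visible |

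**Step 2: ECGs scheduled (12-lead ECG rows of Table 5).** Year 1: Weeks 12, 24 and 52. Year 2: Week 104. Year 3: Week 156. Year 4: Week 208. On-treatment total: 3 + 1 + 1 + 1 = 6. Subjects who stop early also have an ECG at the early termination (ET) visit.

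**Step 3: readings left out.** Assumption: the end of Weeks 0-208 means the last on-treatment reading. With k post-baseline ECGs, the table uses 1 and omits k - 1, a fraction of (k - 1)/k. The baseline ECG does enter the shift table and is not counted here.

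| Time of ET visit | k | Omitted | Fraction |
|---|---|---|---|
| Before Week 12 | 1 | 0 | 0/1 = 0% |
| Weeks 12-24 | 2 | 1 | 1/2 = 50% |
| Weeks 24-52 | 3 | 2 | 2/3 = 67% |
| Weeks 52-104 | 4 | 3 | 3/4 = 75% |
| Weeks 104-156 | 5 | 4 | 4/5 = 80% |
| Weeks 156-208 | 6 | 5 | 5/6 = 83% |
| None (completed Week 208) | 6 | 5 | 5/6 = 83% |

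A subject discontinued at Week 12 under the clinical criteria has 0 of 1 omitted if that visit serves as the ET visit, or 1 of 2 if the ET visit is separate.

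These are counts from the schedule, not observed data. They leave out ECGs taken at unscheduled visits, which Protocol 6.2.1 allows.

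**Step 4: what else could show the omitted readings.** For ECGs judged abnormal and clinically significant, Protocol 6.5.2 says that "results if not related to medical condition or diagnosis, should be recorded as an AE on the AE eCRF". Protocol 6.5.4 agrees: "Clinically significant abnormal findings or results, not related to a medical condition or diagnosis, during this study should be recorded as AEs". Where a diagnosis explains the finding, Protocol 10.1 has the diagnosis recorded as the adverse event. Clinically significant findings can therefore reach the adverse event tables in SAP 12.2. Abnormal readings judged not clinically significant have no such route.

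**The case against.** The strongest objection is redaction. SAP Section 2 says early termination changed some protocol-specified analyses and that Section 16 summarizes the changes. Two of the three bullets there are blacked out, and the readable one concerns interim analyses. Either hidden bullet could cover ECG, and other SAP text is also unseen. This stands: the reduction cannot be called undeclared. It does not change what the table can show, and no redaction is marked within 12.5. Nor does early termination by itself explain the choice, because the same SAP keeps by-visit summaries for laboratory data, vital signs and weight.

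Second, Protocol 9.1 leaves details to the SAP, and 9.7 does not literally require every scheduled visit. The end of Weeks 0-208 is itself one of the SAP's time points. That is a possible reading, but a strained one, since the SAP gives the same sentence a by-visit meaning for the other three parameters.

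Third, the adverse event tables are a real backstop with a subject denominator. The readable safety endpoint, in Protocol Table 4, refers to clinically significant ECG changes. It is also the adolescent table, the adult row is not visible, and SAP 4.1 says the study supplying adolescents was never initiated. Little weight can therefore rest on that endpoint wording. The concern rests instead on the primary objective and on Protocol 9.7. Adverse event incidence still does not give ECG status by visit.

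Fourth, the fractions hold for any last-reading table and prove no effect on a conclusion. That is correct. They show how much is set aside, not how often it would matter.

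**Conclusion.** The concern holds on the visible text. Protocol 9.7 calls for ECG summaries by time point, and SAP 12.5 gives a single shift to the end of Weeks 0-208 with no scheduled visit.

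A subject with one post-baseline ECG loses nothing; a subject with two or more loses all but the last. Because the study was terminated early, the shorter-exposure rows are probably the relevant ones. The 80% and 83% rows need more than 104 and more than 156 weeks on study respectively, and no document shows that anyone got that far.

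The counts assume that the end of the period means the last on-treatment reading. The documents give no ECG abnormality rate, so the number of subjects misrepresented is unknown. This is a worthwhile improvement to the safety reporting rather than a flaw that threatens the study's conclusions.

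**What to change.** In SAP 12.5:

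1. Tabulate the three-category ECG interpretation by scheduled visit, with the number of subjects assessed at each visit, in line with Protocol 9.7.
2. Keep the shift from baseline to the end of Weeks 0-208, and define that time point if the full SAP does not already do so.
3. Add a shift from baseline to the worst post-baseline interpretation. The protocol does not promise this; it is an improvement modelled on what SAP 12.3 does for hematology and chemistry.

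If the by-visit summary was dropped on purpose, Section 16 should say so and give the reason, unless a redacted bullet already does.

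The cost is two extra tables from interpretations already held in the eCRF, with no new assessment or data collection.
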